Because of the importance of women's health to the VA, we will oversample women to ensure that 25% of the sample (n=70; approximately the total number of participants in the JAMA 2008 or JGIM 2011 reward trials) will be women and then stratify by gender. To enroll 280 Veterans, we can recruit as few as 10 per month per site over 15 months. This is a similar recruitment rate to JAMA (2008) (12/month per site) and a recently funded clinical trial at VA Puget Sound Health Care System (Nelson IIR# 14-063: 390 Veterans over 24 months). By randomizing in blocks of 14 and recruiting at least 20 Veterans per month we ensure that treatment arms will be balanced in terms of the season of the year the participants entered the trial.

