### 5.6.a. Data Analysis

All data will be analyzed at VA Puget Sound Health Care System by one of the data analysts and/or investigators.

We will use an intent to treat analysis. To test each hypothesis we will estimate an equation of the form

$\Delta Y_{it} = \beta_0 + \beta_1 Weight_{i0} + \beta_2 M_i + \beta_3 F_i + u_i$  (1) where  $\Delta Y_i$  is change in weight from baseline to follow-up time t

for patient i;  $Weight_{i0}$  is baseline weight for patient i; F is the financial rewards (arm 2); M is an indicator for assignment to non-financial rewards (arm 3); and u is a random error. To gain a small amount of efficiency we can also estimate (1) using repeated measures of change in weight from baseline to the three follow-up measures (16 weeks, 32 weeks and 12 months) using GEE models of the same form as equation (1), except with dummy variables for follow-up periods and interactions between these variables and the treatment group dummies.

Hypothesis 1a implies a test of superiority and will be assessed using two-sided tests of  $\beta_2 = 0$  for non-financial rewards, and  $\beta_3 = 0$  for financial rewards. Large positive or negative values of  $\beta_2$  and  $\beta_3$  are evidence against the null hypothesis of no difference between reward and non-reward groups.

Hypothesis 1b implies a non-inferiority test. We will reject the hypothesis that non-financial rewards are inferior to financial rewards if  $\beta_2$  is statistically significantly greater than zero (i.e., there was statistically significantly more weight loss in the non-financial reward arm than in usual care) and if  $(\beta_3 - \beta_2) < 2.5 kg$ , where  $(\beta_3 - \beta_2)$  is the adjusted difference in mean weight loss between the financial and non-financial reward arms, and 2.5 kg is half the 5 kg weight loss assumed to be clinically significant. Although there are no defined rules for choosing a range of indifference for a non-inferiority test, researchers often use half the minimum clinically significant amount. Values of  $(\beta_3 - \beta_2)$  that are statistically significantly larger than 2.5 kg are evidence against the hypothesis that non-financial rewards are not inferior to financial rewards.

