Hypothesis 1c implies a test of superiority and will be assessed using two-sided tests of  $(\beta_3 = \beta_2)$  in comparisons of weight change from week 16 to week 32 and 12 months, respectively. We will use weight change at week 16 in place of weight at baseline in equation 1, such that differences in weight regain between treatment arms will be adjusted for weight lost over weeks 1-16.

Because all secondary outcomes are continuous variables, a similar equation will be used to assess changes in secondary outcomes. These analyses explore how rewards affect constructs that are believed to mediate the effect of rewards on weight loss.

Missing weight measures will be imputed using data from patients' medical records for routine medical visits and methods developed and tested via simulation by [name] et al. These methods involve estimating longitudinal mixed-effects linear models of weight collected both through the trial and at routine clinic visits as a function of polynomials of time since enrollment, with random components for patient intercept and time, and using the predicted values from this model for any post intervention day as an estimate of what the patient's weight would have been on that day if he/she kept their follow-up appointment.

We assumed a standard deviation of 11.0 lbs. for weight loss based on the results of the JAMA (2008) and JGIM (2011) trials that were conducted in the VA and demonstrated statistically significant differences in

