weight loss at the end of the reward period. We used a two-sided alpha of 0.025 to account for the multiple comparisons between treatment groups (including for hypotheses 1b and 1c, which compare only two groups). We chose a clinically meaningful minimal detectable difference of 11 lbs. (5 kg). This was the weight loss experienced by the lifestyle management arm of the Diabetes Prevention Program randomized trial, which experienced lower rates of the incidence of diabetes. According to data from the 2012 NHANES, 11 lbs. is 5% of the average weight of 233 lbs. for obese men, and the FDA defines a weight loss drug as clinically effective if mean weight loss in the drug group is at least 5% of baseline weight. With these assumptions we would require full data on 21 patients per treatment arm at follow-up, or 28 assuming 20% loss to follow-up, in order to have 80% power to reject hypothesis 1a. In order to conduct subgroup analyses with reasonable precision, and to increase the power to detect differences in weight regain between reward groups (hypothesis 1c), we will increase enrollment to 80 patients in the no-reward arm, and we will increase the ratio of patients randomized to control versus either reward group from 1:1 to 1:1.25 for a total of 280 patients (80 usual care+100 in each reward arm). This provides a minimum detectable difference of 5.1 lbs. between treatment arms, and 4.5 lbs. if the reward arms are combined. In the three studies in Table 1, the average weight loss in the control groups at the end of follow-up was 1.6 lbs. Thus, we expect 80% power to detect weight loss as small as 6.7 lbs. in each reward group. At the end of the reward period, the average weight losses in the reward groups was 10 lbs. (range, 14 to 3.7) among the trials in Table 1. In the JAMA (2008) study, 50% of the reward group achieved their goal of 16 lbs. weight loss in 16 weeks. Thus, we have the power to detect achievable and clinically important weight losses across treatment arms.

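### The plan stratifies by gender, but Equation (1), its GEE version and the hypothesis 1c model have no gender term; adding one costs one degree of freedom and may gain a little precision

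*Combined protocol and SAP*

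**What the plan says.** Section 5.2.b (under 5.2 Recruitment Methods) states that "we will oversample women to ensure that 25% of the sample (n=70" and so on "will be women and then stratify by gender". The block size comes two sentences later: "By randomizing in blocks of 14 and recruiting at least 20 Veterans per month". The reason given there for the blocks is balance by season of entry, not gender.

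The models are in section 5.6.a:

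- **Equation (1)** regresses weight change on baseline weight and two arm indicators. The terms are defined thus: "is baseline weight for patient i; F is the financial rewards (arm 2); M is an indicator for assignment to non-financial rewards (arm 3". Gender is not among them.
- **The GEE version** has the same form, "except with dummy variables for follow-up periods and interactions between these variables and the treatment group dummies".
- **The hypothesis 1c model** changes one covariate: "We will use weight change at week 16 in place of weight at baseline in equation 1".

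Gender otherwise enters the analysis only through exploratory subgroup work (a female-by-arm interaction). The plan gives no reason for leaving it out of the main models.

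**The concern.** When allocation is balanced within strata and the stratum predicts the outcome, the arm comparison varies less from trial to trial than a model without the stratum assumes. The model counts the between-stratum spread as random error, so its standard errors come out somewhat too large and its intervals somewhat too wide. The design here treats gender as important enough to oversample and stratify on, and the analysis then does not use it.

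At stake is a little precision in every comparison. The non-inferiority test in 1b is the most visible case, since a wider interval is harder to fit inside the 2.5 kg margin. The plan already offers the GEE version for a slight efficiency gain, and a gender covariate is a gain of the same kind.

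**Working it through.** **Inputs from the documents.** 280 participants split 80:100:100; 25% women (70), hence 210 men; blocks of 14; 20% loss to follow-up; 80% power. For the SD, "We assumed a standard deviation of 11.0 lbs. for weight loss". For alpha, "We used a two-sided alpha of 0.025 to account for the multiple comparisons between treatment groups". The gender gap in weight change, d, is not given, so 0, 3, 5 and 8 lb are assumptions.

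**1. Does stratified blocking fit?** The allocation 80:100:100 reduces to 4:5:5, which sums to 14. The strata also divide exactly: 70/14 = 5 blocks and 210/14 = 15 blocks. This fits gender-stratified randomisation but does not prove it.

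**2. Reproduce the plan's figure.** MDD = SD × √(1/n₁ + 1/n₂) × (z₀.₉₈₇₅ + z₀.₈₀). For 100 v 80: 11 × √(0.0100 + 0.0125) × (2.241 + 0.842) = 11 × 0.150 × 3.083 = 5.09 lb (5.12 with the noncentral t). The plan says 5.1. The same formula gives 4.49 lb for combined reward arms (stated 4.5) and 4.80 lb for 100 v 100 (stated 4.8). These figures use the unadjusted SD, so the absence of gender does not make them wrong.

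**3. Largest gain from a gender term.** Variance explained: R² = 0.25 × 0.75 × d² / 11². Standard error ratio: √(1 − R²).

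| Assumed d (lb) | R² | SE ratio | SE reduction | MDD 100 v 80 (t, lb) |
|---|---|---|---|---|
| 0 | 0 | 1.000 | 0% | 5.12 |
| 3 | 1.6875/121 = 1.4% | 0.993 | 0.7% | 5.09 |
| 5 | 4.6875/121 = 3.9% | 0.980 | 2.0% | 5.02 |
| 8 | 12/121 = 9.9% | 0.949 | 5.1% | 4.86 |

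These are ceilings, provided the weight covariate absorbs part of the gap rather than masking it.

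**4. Simulation of Equation (1) under the null.** Gender-stratified 4:5:5 blocks of 14, 80% retention, 6,000 runs per gap. Further assumptions: mean baseline weight 240 lb in men and 205 lb in women, SD 35 lb, and no effect of baseline weight on outcome given gender.

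| d (lb) | Mean model SE, no gender | Mean model SE, with gender | Empirical SE, no gender | Type I error, no gender (nominal 0.025) |
|---|---|---|---|---|
| 0 | 1.848 | 1.850 | 1.855 | 0.027 |
| 3 | 1.846 | 1.837 | 1.825 | 0.022 |
| 5 | 1.842 | 1.812 | 1.847 | 0.026 |
| 8 | 1.834 | 1.755 | 1.773 | 0.021 |

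The model SE falls by about 0.5%, 1.6% and 4.3% at 3, 5 and 8 lb. This is less than step 3 because baseline weight stands in for part of the gender effect. The Monte Carlo error is about 0.002 on the type I error and about 1.85/√12,000 = 0.017 on the empirical SE. So type I error is not inflated, and the excess of model SE over empirical SE stands clear of noise only at 8 lb (1.834 v 1.773).

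**5. Hypothesis 1b.** Margin 2.5 kg = 5.51 lb, one-sided 0.025. With 100 per arm the power is Φ(5.51/(11 × √(2/100)) − 1.96) = Φ(1.58) = 0.94, as stated. After 20% loss (80 per arm) it is Φ(5.51/(11 × √(2/80)) − 1.96) = Φ(1.21) = 0.887. Multiplying the SE by the step 3 ratios gives at most 0.891, 0.898 or 0.916 at 3, 5 or 8 lb.

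**The case against.** The strongest reply is that the premise is inferred. The stratification phrase sits in the recruitment section and does not mention randomisation. The blocks are justified by season, and the places that describe when arms are assigned (sections 5.2.b and 5.5.c) mention no strata. The phrase could instead point to the planned gender subgroup analysis. This stands as far as it goes: stratified randomisation is the natural reading, not a stated fact, and must be confirmed.

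The second reply is that the loss is conditional and small. Precision is lost only if gender predicts weight change beyond baseline weight (or, for 1c, beyond week-16 weight change), and the documents give no figure for this. That also stands. The plan's own 20% attrition moves the detectable difference from about 5.1 to 5.7 lb, more than a gender term does at any gap considered here.

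A reader might infer more than the documents support:

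- **That the standard errors are definitely too large.** At a zero gap they are not.
- **That estimates are biased, tests are anti-conservative or the power figures are wrong.** Omitting a balanced stratum does not bias the arm contrasts, any error is conservative, and the power figures reproduce.
- **That the gender subgroup analysis is mis-specified.** The plan does not write out that model, so nothing shows that it would lack a gender main effect.

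None of this supplies a reason for leaving gender out.

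**Conclusion.** The mismatch holds as a minor point of efficiency and consistency. The plan describes stratification by gender, and none of its three models includes gender. The possible gain in standard error runs from nil to about 5% across the assumed gaps of 0 to 8 lb, and for 1b from nothing to about 3 percentage points of power after the planned attrition (0.887 to 0.916). It rests on three assumptions: that the stratification applies to the randomisation, that women make up about 25% of the sample, and that the SD is 11 lb. The validity of the planned tests is not in question.

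**What to change.** State in section 5.2.b whether the arm randomisation is stratified by gender. If it is, prespecify a gender indicator as a covariate in Equation (1), its GEE version and the hypothesis 1c model, for all hypotheses and at 16 weeks, 32 weeks and 12 months, before outcomes are examined by arm.

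The cost is one degree of freedom and a sentence of text. Gender is already recorded at phone screening (section 5.5.a), so no new data are needed. At a zero gap the penalty is negligible (mean model SE 1.850 v 1.848).

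If randomisation turns out not to be stratified, the argument from the design falls away. Gender could still be prespecified as a prognostic covariate: the same simulation without stratification gives similar reductions in model SE (about 0.4%, 1.4% and 4.1% at 3, 5 and 8 lb). In that case it is an optional choice.

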### 5.2.c. Participant payments.

Participant payments are shown in Table 3.

Table 3. Participant maximum possible payments:

	Participation	Assured	Random	Token	Total
No rewards	\$80	--	--	\$100	\$180
Financial rewards	\$80	\$100	\$300	\$100	\$580
Non-financial	\$80	\$100	\$300	\$100	\$580

*No rewards (usual care) group:* To encourage continued participation, usual care participants will be given \$20 for each in-person study visit attended, for a total of up to \$80.

*Financial rewards group:* To encourage continued participation, financial reward participants will be given \$20 for each in-person study visit attended, for a total of up to \$80. They will also have the chance to earn up to \$400 in reward money. They can earn \$100 from monthly assured rewards (4 months x \$25); \$300 in random rewards (three chances to earn \$100 on random, pre-selected weeks; and 4 chances to earn token rewards (t-shirts, movie tickets, etc.) for reporting their weight in weeks 17-32, with an approximate value of \$25 each.

*Non-financial rewards group:* To encourage continued participation, non-financial reward participants will be given \$20 for each in-person study visit attended, for a total of up to \$80. They will also have the chance to earn up to approximately \$400, or 80 points, worth of non-financial rewards (each point is worth approximately \$5. They can earn 20 points from monthly, assured rewards (4 months x 5 points), plus 60 points in random rewards (three chances to earn \$100 on random, pre-selected weeks. These are not cumulative. If they meet all their goals they will receive a total of seven rewards. They will also have 4 chances to earn token rewards (t-shirts, movie tickets, etc.) for reporting their weight in weeks 17-32.

There is a delay in financial payment that is beyond our control. Due to VA Puget Sound facility policies and practices all financial payments will be processed through the Austin Payment Center. Unfortunately, this process often takes up to three months. All participants will be made aware of this delay.

Real SSNs will be collected for payment purposes, but will be stored separately from study data.

### 5.3 Informed Consent Procedures

For recruitment purposes, we will seek a waiver of informed consent and a waiver of HIPAA authorization. At enrollment, participants will need to complete an informed consent form and HIPAA authorization to participate in the study.

Informed consent and HIPAA authorization will be obtained by the Principal Investigator, qualitative researcher, study coordinators or qualitative analyst/coordinator. The study staff obtaining consent will be trained to provide adequate time and opportunity for the participant to consider all options, respond to the participant's questions, ensure that the participant has comprehended this information, obtain the participant's voluntary agreement to participate, and continue to provide information as the participant or situation requires. We will ensure there is opportunity for the researcher and the participant to exchange information and ask questions.

## 5.4 Inclusion/Exclusion Criteria

### 5.4.a. Inclusion criteria.

Determined through CPRS, VistA, CDW or VSSC:

- Age 18-69
- Weight <390
- BMI  $\geq 30$  (weight (kg)/height(m^2))
- Active patient in primary care or women's clinic (1+ visit in last two years)
- Primary care/women's clinic visit located at the following VAPSHCS locations: Seattle, American Lake, Bellevue CBOC, Federal Way CBOC, Seattle (Lake City) CBOC or Bremerton CBOC

The inclusion for weighing less than 390 pounds is because the scales that we can economically provide are rated for 400 pounds or less, and we want to expand the criteria to include as many participants as possible. The inclusion of BMI  $\geq 30$  (kg/m^2) ensures that the target weight loss of 1 lb. per week is safe and beneficial for all Veterans. Enrolling Veterans age < 70 is because the evidence for the benefit of weight loss age 70+ is relatively weak. We are excluding patients with primary care/women's clinic visits at sites other than those listed above because participants are only being paid \$20 for each visit and expecting participants to drive for > 2 hours one-way (or 4 hours round trip) seems unreasonable and inadequate.

### 5.4.b. Exclusion criteria.

Determined through CPRS, VistA, CDW or VSSC:

- Behavioral flag
- Diagnosis of eating disorder, PTSD with sexual trauma, Serious Mental Illness (SMI; see ICD-10 exclusions below) or antipsychotic medication
- MOVE! participation in past 4 months
- Pregnant
- Prisoner
- Using insulin to treat diabetes
- Homeless

Patients with a behavioral flag will be excluded because of potential disruption to study procedures and randomization. The exclusion for serious mental illness (SMI) is because antipsychotics cause weight gain, and consequently Veterans with SMI benefit from specific training for weight loss. We will exclude Veterans with the following ICD-10 diagnosis codes: F30.2: Manic episode, severe with psychotic symptoms; F31.2: Bipolar affective disorder - current episode without psychotic symptoms; F31.5: Bipolar affective disorder - current episode severe depression with psychotic symptoms; F32.2: Severe depressive disorder without psychotic symptoms; F32.3: Severe depressive disorder with psychotic symptoms; F33.3: Recurrent depressive disorder, current episode with psychotic symptoms. Veterans with serious mental illness including bipolar, schizophrenia and a recent history of suicidality or psychiatric hospitalization will be excluded as determined by chart review. Patients with a diagnosis of PTSD will be evaluated on a case-by-case basis by the study clinician and the patient's mental health and primary care provider to determine the appropriateness

of participation. To avoid adverse effects of rewards, we will exclude Veterans with documentation in chart notes of eating disorders, or Veterans with PTSD and a history of sexual trauma, who may have issues regarding body image. The restriction that Veterans have no MOVE! participation in the prior 4 months is to ensure that we do not recruit active MOVE! group participants. The MOVE! meeting dynamics may be adversely affected if some of the Veterans are receiving rewards for weight loss. Women currently pregnant will also be excluded due to potential risks of losing weight. Prisoners are excluded because they must be able to come in for in person weigh-ins. If a potential participant is an employee or student we will not exclude them based on this information. We do not have compelling evidence that participation in this trial would impact their status as an employee or student. Veterans currently taking insulin for diabetes are excluded due to insulin's effects on weight loss. Homeless patients are excluded due to the numerous mailings that are involved in participating in this study. There may be additional conditions identified during chart review indicating that a Veteran may not be an appropriate fit for the study. In these cases, the charts will be reviewed by the Principal Investigator or the study clinician in order to determine potential eligibility.

Determined or confirmed after chart review, patient self-report:

- Blindness
- Inability to read
- Cognitive impairment
- Inability to remove socks and shoes
- Inability to stand independently
- No access to a phone in the Veteran's household
- Pregnant or planning pregnancy in the next 12 months
- MOVE! participation in past 4 months
- Using insulin to treat diabetes
- No availability or willingness to come to VA (American Lake or Seattle) for research purposes
- Indicator that they do not live at the same place for the entire year\*
- No phone that can receive a text message or no email address
- No routine internet access

The exclusion for blindness and inability to read is necessary because the participants will be given MOVE! workbooks as part of the intervention, and will be required to read a home digital scale. Patients with impaired decision making will be excluded because patients need to have fully cognition of the choices they are making in this study. The inability to remove socks and shoes is included because it is a requirement to successfully use the scale. Participants will also need to independently stand on the scale without assistance which could modify the recorded weight. Access to a text capable phone is necessary to receive study reminders. Routine access to the internet is necessary to update weekly weight and participate in the four patient surveys.

If text messages are the patient's preferred method of reminders, text messages will be sent to participants' phones using the VA Outlook system. This will be done by adding their cell phone carrier's unique email address to their phone number. The general format will be [[contact]](mailto:[contact]). For example for AT&T it would be [[contact]](mailto:[contact]), Verizon [[contact]](mailto:[contact]), T-Mobile [[contact]](mailto:[contact]), etc. From our perspective, it will look as though we are sending an email, while they receive a text message. We will do this from our study email account: [[contact]](mailto:[contact]). Participants will not be able to respond to text messages. Text messages will only be used as reminders (Appendix V). If a patient prefers, we will send reminder emails in lieu of text messages, which includes the portal URL. If a participant has cricket wireless they will have to receive email reminders because text messaging does not work on cricket wireless. If the participant doesn't have an email then they will not receive weekly reminders. We will use the study email address to email participants. Participants will not be able to respond. All text messages and emails will note that any responses will not be seen. The emails will contain the required email disclaimer (Appendix V).

The above exclusion and inclusion criteria are patterned on those used in the Journal of the American Medical Association (JAMA) and Journal of General Internal Medicine (JGIM) trials that were conducted in the VA. We want to capture patients that are willing to participate in the in person study visits and we want patients that

live in the area year round. We are trying to screen out “snow birds,” or patients who live in the area only part of the year. However, eligibility will be determined on a case-by-case basis, depending on if patients will be in the area for the 4 in-person study visits at baseline, 16 weeks, 32 weeks, and 1 year.

